12.5 Analysis of Primary Endpoint

The primary study endpoint will be evaluated by a one-sided exact test of the VESUVIUS Demineralized Fibers and the EVEREST Spinal System combination success rate against the literature success rate of 74.3% with a non-inferiority margin of 10% at a significance level of 0.05. If the lower bound to the exact one-sided 95% Confidence Interval of the VESUVIUS Demineralized Fibers and the EVEREST Spinal System combination success rate is greater than 64.3%, the primary endpoint will have been met.

12.6 Safety Analyses

Incidence rates of adverse events will be provided descriptively in tabular form for each study groups for the overall adverse event rate, serious adverse event rates, revision rates, removal rates, etc. at each follow-up interval.

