8 STUDY ENROLLMENT/EVALUATIONS

8.1 Patient Screening and Enrollment

Consecutive patients who potentially meet the study inclusion and exclusion criteria will be screened for eligibility. The screening process will be as follows:

- Consecutive patients are potentially eligible for entry into the study based on their age and whether their medical condition appears to generally fit the characteristics specific to this study.
- Patients who agree to enter the study must sign the approved informed consent form.
- A patient is considered enrolled in the study after signing the IRB approved informed consent. Consented patients complete the remainder of the screening process to confirm study eligibility. Patients who do not fulfill the screening criteria are considered Screening Failures and will be documented on the Screening and Enrollment Log. Screening failures will not count against the total number of subjects eligible for analysis.
- Diagnostic imaging studies (standing x-rays) MUST be completed within 180 days of the planned surgery. For diagnostic purposes, an optional pre-op MRI may also be done, per surgeon's standard of care, but does not serve as a substitute for standing x-rays.
- Subject self-assessment questionnaires must be completed within 90 days of the planned date of surgery.
- Subjects who have signed the informed consent and fulfilled the Inclusion/Exclusion criteria are then scheduled for surgery.
- If study surgery is unable to be completed within 90 days of the date of screening, the patient self-assessment questionnaires must be repeated and the site must assess whether any imaging studies need to be repeated (these must be dated within 180 days of surgery). If any imaging study is outside the screening window and has to be repeated, the subject must be exited from the study, re-consented, and assigned a new Subject ID number for re-screening. The Screening Log will provide a means to identify the original Subject ID number for any subjects who are rescreened.

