Additional post-operative restrictions may be imposed according to the standard of care normally utilized by the Investigator. In addition, subjects should be instructed to notify the Investigator if experiencing untoward events including but not limited to noticeable pain, numbness, tingling, or weakness that does not decrease with rest, swelling of the lower extremities that does not decrease, or increased pain, erythema, edema or drainage from the surgical incision. The Investigator should then determine if an evaluation is warranted.

A Subject may be withdrawn from the study intra-operatively at the discretion of the Investigator if unexpected findings/occurrences dictate deviation from the intended study procedure. Justification for an intra-operative withdrawal and alternative surgical procedure must be fully documented in the subject's medical record and on the Study Exit case report form.

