9 ADVERSE EVENTS

9.1 Definitions

9.1.1 Adverse Event

An Adverse Event (AE) is defined as any untoward medical occurrence in a subject undergoing surgery in this trial which does not necessarily have a causal relationship with this intervention. An AE can, therefore, be any unfavorable and unintended sign (including an abnormal laboratory finding), symptom, or disease temporally associated with the use of the one of the devices, whether or not the event is considered causally related to the use of the device. Any worsening of a pre-existing condition or illness is considered an AE. Laboratory abnormalities and changes in vital signs are considered to be AEs only if they result in discontinuation from the study, necessitate therapeutic medical intervention that could impact the study's surgical outcomes, and/or if the Investigator considers them to be AEs.

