12.4 Analysis Populations

Analysis Populations are defined as follows:

- The Intent-to-Treat (ITT) population includes all enrolled subjects.
- The Per-Protocol population includes all enrolled subjects who have no major protocol violations (defined as not meeting inclusion/exclusion criteria or not being consented properly).

The fusion analysis will be performed on the ITT population. Analysis of the per-protocol population will be confirmatory of the ITT analysis. The safety analysis will be performed on the ITT population.

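### Safety rates are set on all consented subjects with no stated denominator per interval; a surgery-started safety set and numbers at risk are needed to avoid dilution

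*Combined protocol and SAP*

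**What the plan says.** Section 12.4 assigns the safety population: "The safety analysis will be performed on the ITT population". It defines that population in the same section: "The Intent-to-Treat (ITT) population includes all enrolled subjects". Section 8.1 fixes the moment of enrolment: "A patient is considered enrolled in the study after signing the IRB approved informed consent". This comes before eligibility is confirmed and before surgery.

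Section 8.1 also limits the count: "Screening failures will not count against the total number of subjects eligible for analysis". Section 12.4 does not repeat that exclusion. For a subject whose imaging falls outside the screening window and must be repeated, section 8.1 says "the subject must be exited from the study, re-consented, and assigned a new Subject ID number for re-screening". It does not say whether the first ID is then a screening failure.

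On the numerator, section 9.1.1 defines an adverse event as "any untoward medical occurrence in a subject undergoing surgery in this trial", and the schedule in section 8.6 starts adverse event assessment at the operative stage. Section 9.1.3 defines revision, removal and supplemental fixation in relation to the implanted system, and reoperation as surgery at the involved level.

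Section 12.6 calls for descriptive tables of "serious adverse event rates, revision rates, removal rates, etc. at each follow-up interval". It names no denominator, number at risk, person-time or time-to-event method. No safety or as-treated set is defined anywhere.

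**The concern.** The numerator is confined to people who had the operation, while the denominator, read literally, is everyone who consented and was not a screening failure. A person who qualifies, consents and then withdraws before surgery adds to the denominator and cannot add to the surgical numerators. Error from this source can only lower the reported rate.

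A second gap concerns time. Rates are promised by interval, but the plan does not say whether a subject who left before an interval still counts in it. Whoever builds the tables could keep the full enrolled number or use those still followed, and could decide after seeing the data.

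Adverse events and additional surgery at the operative site are the primary safety objectives (section 5.2). Because safety is reported descriptively, with no test or interval estimate, the tabulated percentage is the whole safety result.

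**Working it through.** **The plan's own safety figures.** Section 12.3 gives the chance of seeing at least one serious event with 204 subjects. Using 1 − (1 − p)^n:

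- p = 0.8%: 1 − 0.992^204 = 80.6% (plan: above 80%).
- p = 1.0%: 1 − 0.990^204 = 87.1% (plan: 87%).

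Both reproduce if all 204 are operated on and observed. With 173 observed (204 × 0.85 = 173.4) they become 75.1% and 82.4%. That change comes from the number observed, not from the denominator of a reported rate, so it is context and does not measure the present problem.

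**Inputs for the dilution.**

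- N = 204 and 15% dropout: section 12.3.
- True interval rate among subjects operated on and still followed: 5.0%, an illustration.
- Share of enrolled subjects never operated on, u: not in the documents; assumed 0%, 5% or 10%.
- Share of operated subjects gone before the interval starts, x: 0%, or 15% if the whole allowance is spent by then.

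**Formula.** If every enrolled subject stays in the denominator, reported rate = true rate × (1 − u) × (1 − x).

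Example with u = 0 and x = 15%: 173.4 followed × 5.0% = 8.67 events; 8.67 / 204 = 4.25%.

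| Never operated (u) | Exited (x) | Factor | 5.0% is reported as |
|---|---|---|---|
| 0% | 0% | 1.000 | 5.00% |
| 5% | 0% | 0.950 | 4.75% |
| 10% | 0% | 0.900 | 4.50% |
| 0% | 15% | 0.850 | 4.25% |
| 5% | 15% | 0.8075 | 4.04% |
| 10% | 15% | 0.765 | 3.83% |

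The relative understatement runs from zero to 23.5%. With subjects operated on and under follow-up as the denominator, the result is 5.0% in every row.

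**What the rows rest on.** Rows with x = 0 follow from sections 8.1 and 12.4 once u is assumed. Rows with x = 15% also need the full enrolled number to be kept at every interval, which the plan does not say. They are an extreme as well, since they place all dropout before the interval begins. The last two rows treat never-operated subjects as additional to the 15%. Because enrolment is at consent, the allowance may already include them; in that case the factor stays at 0.85.

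**The case against.** A reader might infer that the plan orders exited subjects to be carried into later intervals, and that its rates will therefore be understated by roughly a fifth. The documents do not support this. Section 12.4 names an analysis set; it does not fix one N for all visits, and a table on the ITT set can still show the number followed. Section 12.6 is silent. The 19% to 23.5% figures also need an unsourced never-operated share, possibly counted twice against the dropout allowance.

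Other text favours a treated-patient reading. Section 4.2 describes the treatment group as patients treated with the products, section 12.6 refers to study groups, and section 9.1.1 ties adverse events to surgery. Section 8.1 removes screening failures, plausibly the largest group never operated on.

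Intra-operative withdrawal is allowed ("A Subject may be withdrawn from the study intra-operatively at the discretion of the Investigator"), but those subjects are not empty denominators: section 8.3.1 requires intra-operative adverse events to be recorded. They belong in the peri-operative rates.

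Finally, the analysis is descriptive. No threshold, alpha or power depends on it, and the absence of Kaplan-Meier estimates from a descriptive table is not in itself an error.

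All of this stands as a limit on size and certainty. It does not remove the mismatch: the only population sentence for safety still points to all enrolled subjects, the screening-failure rule does not cover eligible subjects who never reach surgery, and the interval denominator is still open.

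**Conclusion.** The point holds in a limited form. Read literally, sections 8.1 and 12.4 put eligible but never-operated subjects, and possibly the first ID of a re-screened person, into the safety denominator. That can only lower rates of surgical events. Separately, section 12.6 leaves the interval denominator unstated.

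On the plan's own 15% allowance, a true 5.0% rate would be shown as no lower than 4.25% because of exits, and only if the full enrolled number were kept throughout. Each 5% of enrolled subjects never operated on, if additional to that allowance, takes off about another 5% in relative terms. With everyone operated on and followed there is no bias. Whether rates will in fact be understated cannot be said from the documents. The fusion test, its alpha and its power are not touched. The change is still worth making, because the safety percentages stand alone and the ambiguity is cheap to remove.

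**What to change.** - **Section 12.4:** replace ITT for safety with a safety set of all subjects in whom the study surgery was started. Keep intra-operative withdrawals for peri-operative events. Count each person once, whatever the number of IDs. Carry over the screening-failure exclusion from section 8.1 and state the status of a re-screened subject's first ID.
- **Section 12.6:** use, and print in each table, the number under follow-up at the start of each interval as that interval's denominator.
- **Section 12.6:** add Kaplan-Meier 24-month cumulative rates for revision, removal, supplemental fixation and reoperation, censored at last contact. A crude cumulative proportion is lowered by loss to follow-up even when only operated subjects are counted.

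The cost is SAP wording and a little more table work, with no new data collection. Reported rates may come out slightly higher.

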12.7 Supplementary Analysis

Other ancillary variables such as demographics, baseline variables, surgical variables and post-op pain medication usage will be summarized by mean, standard deviation, median (if appropriate), and range for continuous measures, and frequency and percent for categorical measures. Descriptive statistics and graphical methods such as bar graphs, box and whiskers plots, and star plots may be employed to compare subjects' clinical outcomes to baseline values (pre-operative) and the prospective and historical study groups simultaneously for multiple variables.

Descriptive statistics or graphical methods will also be used to explore the impact of any covariates of interest, e.g., presence or absence of anterior spacer on the prospectively collected outcome data.

12.8 Methods to Minimize Bias

This trial includes several well-validated patient-reported outcome measures (i.e., ODI, VAS, and SF-12v2). When providing follow-up self-reports of these outcomes, subjects will remain blinded to their previous responses on these instruments so as to not bias their current reports. With respect to the SF-12v2, previously published validation studies have shown that the results of this instrument, particularly the physical functioning domains, are not substantially affected by non-specific study effects such as placebo. When conducting follow-up neurological examinations, every effort will be made to blind the investigators to the ratings provided at earlier

intervals. Investigational sites will be restricted from enrolling more than approximately 15% of the study cohort. Radiographic evaluations will be conducted by an independent central radiologist.

We will evaluate the subjects from each site to assess poolability of the data. Sites will be examined for adherence to the requirements of the protocol, baseline demographic and relevant clinical characteristics.

13 SITE RESPONSIBILITIES

13.1 Investigator

Principal Investigators selected by K2M to participate in this clinical study assume overall responsibility for the performance of the study at the site.

Specifically, the Investigator will assume the overall responsibility for:

- Obtaining IRB approval
- Conducting the study according to the clinical protocol and applicable, federal, state and local regulations and the signed Clinical Research Agreement
- Providing financial disclosure according to federal regulations
- Proper execution of the approved informed consent
- Protecting the rights, safety and welfare of study subjects
- Appropriate source documents to verify study data
- Reviewing and signing all CRFs for subjects enrolled in the study
- Oversight and training of site staff given study related responsibilities

13.2 Study Coordinator

The Study Coordinator is designated by the Investigator to assume site management responsibilities. Specifically, the Study Coordinator is responsible for:

- Managing the IRB submission and approval process
- Managing study activities according to the clinical protocol and applicable, federal, state and local regulations and the signed Clinical Research Agreement
- Ensuring proper execution of the approved informed consent
- Protecting the rights, safety and welfare of study subjects
- Maintaining appropriate source documents to verify study data
- Ensuring that CRFs are complete, reviewed and signed by the Investigator at the completion of patient contacts and before scheduled monitoring visits
- Management of additional staff members given study related responsibilities

If the Investigator designates a replacement Study Coordinator at any time during the performance of the study, the Sponsor must be notified immediately. A Sponsor designee will arrange to visit the site as soon after the notification as is feasible to ensure that the replacement Study Coordinator has the ability and is adequately trained to function in that capacity.

14 RECORDS AND REPORTS

All Sponsor and site records may be subject to regulatory inspection and must be retained for a period of 2 years following, a) the date the investigation is completed or terminated, or b) the records are no longer required to support a regulatory submission, whichever is longer. The Sponsor will notify the site in regard to length of record retention at the completion of the study.

14.1 Investigator/Site Records

Investigator/site records must be maintained and updated as necessary. Records will be reviewed during the site initiation visit and on subsequent monitoring visits to ensure adequacy and completeness of records. Investigator/site records include, but may not be limited to:

- Original and all subsequent IRB approval letters
- Original and all subsequent (if applicable) approved informed consents
- IRB Roster
- IRB updates/reports as required by reviewing IRB
- Final protocol and subsequent (if applicable) protocol amendments
- Other required reports
- Relevant correspondence between the Investigator, IRB and K2M
- Signed Clinical Research Agreement
- Investigators Agreement for Principal and Sub-Investigators, as required
- Financial Disclosure Documents
- Copies of Curriculum Vitae for the Investigator and Sub-Investigators
- Site Signature & Responsibility Log
- Site Monitoring Log
- Signed Informed Consents
- Completed Case Report Forms

14.2 Investigator/Site Reports

The Investigator/site is responsible for the preparation and submission of reports to the Sponsor, IRB and applicable Regulatory agencies. The following reports are required:

Serious Adverse Events: Submitted to the Sponsor within 10 working days of first learning of the event and to the reviewing IRB as required

Withdrawal of IRB approval: Sponsor must be notified within 5 working days

IRB Updates/Reports: Submitted to the reviewing IRB as required

Failure to Obtain Informed Consent: Submitted to the Sponsor and reviewing IRB within 5 working days after realizing the failure

Final Report: Submitted as required to the reviewing IRB

14.3 Sponsor Records

The Sponsor will maintain site specific study files including:

- Copy of the original and all subsequent IRB approval letters
- Copy of the original and all subsequent (if applicable) approved informed consents
- IRB Roster
- Copy of IRB updates/reports as required by reviewing IRB
- Other required reports
- Relevant correspondence between the Investigator, IRB and K2M
- Signed Clinical Research Agreement
- Investigators Agreement for Principal and Sub-Investigators, as required
- Clinical Research Agreement and Investigators Agreement template, as applicable
- Financial Disclosure Documents
- Copies of Curriculum Vitae for the Investigator and Sub-Investigators
- Copies of site approved recruitment and patient information documents
- Site Initiation Report
- Site Monitoring Reports
- Completed Case Report Forms

In addition, the Sponsor will maintain a Study Central File including, but not limited to:

- Final protocol and subsequent (if applicable) protocol amendments
- Investigator agreement template
- Master recruitment and patient information documents (if applicable)
- Composite listing of adverse events
- Data and data analysis
- Interim (if applicable) and final summary

14.4 Sponsor Reports

The Sponsor is responsible for the preparation and submission of reports to the site and applicable Regulatory agencies. The following reports are required:

Serious Adverse Events: Submitted to the FDA only if they meet the requirements for MDR reporting

Final Report: Submitted to all sites upon completion of the study and final data analysis

Reports not listed may be made by the Sponsor to Regulatory agencies and to the sites if additional notifications are necessary.

15 PUBLICATION POLICY

Data resulting from the conduct of this study are considered confidential information. Abstracts, book chapters, peer-reviewed manuscripts and other publications (all of which are "Publications") resulting from the study can originate from the Sponsor or from Investigators participating in the study; provided, however, any Publications shall be governed by and in compliance with the terms of Section VIII of the Clinical Evaluation Research Agreement.

APPENDIX 1 – Bone Marrow Aspiration & Hydration of VESUVIUS Demineralized Fibers

NOTE: VESUVIUS Fibers are packaged in quantities of 2, 5, 15, and 30 cc; use this to help estimate the volume of local bone used

Bone marrow aspiration from the posterior or anterior iliac crest is performed as follows:

1. Locate site for aspiration of bone marrow.
2. Using sterile technique, prepare surgical site and anesthetize the area.
3. With a scalpel, make incision in the skin above the area from which the bone marrow is to be aspirated.
4. Hold needle with proximal end in palm and index finger against the shaft near the tip. This position stabilizes the needle and enhances needle control.
5. Introduce needle through prepared incision site.
6. Use gentle, but firm pressure to advance the needle. Rotate needle in alternating clockwise-counterclockwise motion, or gently tap the needle handle with a mallet. In general, decreased resistance is encountered upon entrance into the marrow cavity.
7. Remove stylet by rotating upper section of handle and pulling stylet straight out.
8. Screw the distal end of the included syringe into the proximal hub of the bone-marrow aspiration needle. Ensure a firm fit, but do not over-tighten.
9. Apply suction by withdrawing syringe plunger to draw bone marrow aspirate (BMA) into the syringe.
NOTE: If using a multi-fenestrated bone-marrow aspiration needle, withdraw no more than 10ml BMA from each harvest site. If using a non-fenestrated bone-marrow aspiration needle, withdraw no more than 2ml BMA from each harvest site.
10. VESUVIUS Demineralized Fibers graft material and BMA should be combined in a 3:2 volumetric ratio (approximately 15cc Fibers and 10ml BMA required for a one-level case). Supplement the BMA with venous-line blood if BMA volumes are insufficient to achieve a 3:2 ratio. **NOTE:** A 1:1 ratio of Fibers:BMA tends to yield an overly wetted final graft construct. This mixture is added to extend local bone for grafting.
11. Disengage syringe containing the aspirated bone marrow and immediately transfer the aspirated bone marrow from the syringe onto the VESUVIUS Demineralized Fibers. Dispose of the needle in accordance with applicable laws and regulations.

Marrow aspiration from the vertebral body is performed as follows:

1. Access the vertebral body via transpedicular technique.
2. Use gentle, but firm pressure to advance the needle through the pedicle into the vertebral body. Rotate needle in alternating clockwise-counterclockwise motion, or gently tap the needle handle with a mallet. In general, decreased resistance is encountered upon entrance into the marrow cavity.
3. Remove stylet by rotating upper section of handle and pulling stylet straight out.
4. Screw the distal end of the included syringe into the proximal hub of the bone-marrow aspiration needle. Ensure a firm fit, but do not over-tighten.
5. Apply suction by withdrawing syringe plunger to draw bone marrow aspirate (BMA) into the syringe.
NOTE: If using a multi-fenestrated bone-marrow aspiration needle, withdraw up to 8ml BMA from each pedicle (16ml total from each vertebral body). If using a non-fenestrated bone-marrow aspiration needle, eight discrete 2ml aspirations can be harvested from each vertebral level – four

from the right and four from the left pedicle, using a coaxial transpedicular technique. Collect aspirates from each of four vertebral depths, one at the superficial depth just beyond the origin of the pedicle from the back of the vertebral body (30mm) and the others from the subsequent depths of 35mm, 40mm, and 45mm of cannula insertion. This technique will yield up to 16ml of bone-marrow aspirate from each vertebral body.

6. VESUVIUS Demineralized Fibers graft material and BMA should be combined in a 3:2 volumetric ratio (approximately 15cc Fibers and 10ml BMA required for a one-level case). Supplement the BMA with venous-line blood if BMA volumes are insufficient to achieve a 3:2 ratio. NOTE: A 1:1 ratio of Fibers:BMA tends to yield an overly wetted final graft construct. This mixture is added to extend local bone for grafting.
7. Disengage syringe containing the aspirated bone marrow and immediately transfer the aspirated bone marrow from the syringe onto the VESUVIUS Demineralized Fibers. Dispose of the needle in accordance with applicable laws and regulations.

